10.1 Definitions

The following definitions will be used in the assessment of safety:

ACP is a standard part of clinical care for patients. The caregiver survey, however, is purely a research activity. We have had excellent experiences with prior caregiver surveys. At the same time, it is possible that this survey could make these subjects upset as they consider advance care planning issues for their family member. In the context of this study, an expected adverse event would be if the participant became distraught during the survey administration, to the point of not being able to complete the survey, or asking to end the survey prematurely. In this unlikely event, the event will be documented on an AE Reporting Form and reported per the guidelines outlined below. We do not anticipate any Serious Adverse Events.

Unanticipated Problem is defined as an event, experience or outcome that meets **all three** of the following criteria:

- is unexpected; AND
- is related or possibly related to participation in the research; AND
- suggests that the research places subjects or others at a greater risk of harm (including physical, psychological, economic, or social harm) than was previously known or recognized.

Possibly related means there is a reasonable possibility that the incident, experience, or outcome may have been caused by the procedures involved in the research

Unexpected means the nature, severity, or frequency of the event is not consistent with either:

- the known or foreseeable risk of adverse events associated with the procedures involved in the research that are described in (a) the protocol-related documents, such as the IRB-approved research protocol, any applicable investigator brochure, and the current IRB-approved informed consent document, and (b) other relevant sources of information, such as product labeling and package inserts; or
- the expected natural progression of any underlying disease, disorder, or condition of the subject(s) experiencing the adverse event and the subject's predisposing risk factor profile for the adverse event.

10.2 Safety Review

Both the risks listed in Section 6.1 and unknown risks will be monitored as follows:

Participants will be informed that they may decline to answer any question that makes them feel uncomfortable. If any adverse events occur, the Principal Investigator will be notified as soon as possible and a corrective plan will be developed and put to use. All AEs will be reported to the IRB at each continuing review.

10.3 Reporting Plans

The Principal Investigator at the site where the event occurred will report Unanticipated Problems, safety monitors' reports, and Adverse Events to the local IRB in accordance with IRB policies:

- Unanticipated Problems involving a fatal or life-threatening event will be reported to the local IRB and to the IRB of record (BMC/BUMC IRB) within 2 days of the site Principal Investigator learning of the event.
- Unanticipated Problems not involving a fatal or life-threatening event will be reported to the local IRB within 7 days of the site Principal Investigator learning of the event.
- Reports from safety monitors with recommended changes will be reported to the IRB within 7 days of the investigator receiving the report.
- Adverse Events (including Serious Adverse Events) will be reported in summary at the time of continuing review, along with a statement that the pattern of adverse events, in total, does not suggest that the research places subjects or others at a greater risk of harm than was previously known.
- Reports from safety monitors with no recommended changes will be reported to the IRB at the time of continuing review.
- When reporting to the local IRB the site Principal Investigator will also report to the administrative study Principal Investigator [name]. Such reporting will also include all findings and determinations made by local IRBs.

The Principal Investigator will report Unanticipated Problems and Adverse Events to the Data Safety Monitoring Board at each bi-monthly Board meeting or as established in the DSMB charter.

The Data Safety Monitoring Board will communicate its reports and recommendations per IRB policies, the DSMB charter, and the study Sponsor.

Per the DSMB charter, the Board will meet every six months to review safety issues and study progress.

10.4 Stopping Rules

The study has no preset stopping rules.

11 Data Handling and Record Keeping

11.1 Confidentiality

Aim 1 Data: Each site (BMC and North Shore Hospital) will collect identifiable EHR data for all eligible patients as described above. All patients will be assigned a unique identifier, and each site will retain a linking file that will not be shared outside of the institution, and will only be accessible to authorized study personnel. At BMC, all data will be stored in password-protected

files on a network server located inside the BMC firewall, which is in compliance with data storage requirements for PHI as defined by BMC. At North Shore, all data will be stored on an excel spreadsheet that is password protected on Microsoft OneDrive. OneDrive is a HIPAA compliant platform for data storage and sharing and has been vetted by Northwell Health's Research IT and Research Compliance teams.

At both sites, any paper records containing study data will be stored in a locked cabinet that is only accessible by the study team. Research participants will be given unique study IDs upon enrollment. The links between participants and their identities will be kept on password protected excel sheets on that are also restricted to authorized study personnel. Data that is shared with external collaborators will be de-identified prior to sending and at least two members of the study team will review the data to confirm that no PHI is present.

All data transfers will be via secure cloud link such as Box.com.

Aim 2 Data: All survey data collected at both sites will be entered into a REDCap project housed at BUMC. Patients will be identified by unique identifier only, but a separate linking file (not in REDCap) will be kept at each site and not shared outside the institution. This linking file will be used to link survey data to the associated patient EHR data. When this data is shared with BMC for data analysis, only a HIPAA LDS will be transferred via secure cloud link such as Box.com.

The study monitor or other authorized representatives of the sponsor may inspect all documents and records required to be maintained by the investigator.

11.2 Source Documents

Source documents for this study will consist of electronic health record (EHR) data from each data collection site (Boston Medical Center and Northshore Medical Center). Data generated by the methods described in the protocol will NOT be recorded in the subjects' medical records and/or study progress notes. Data may be transcribed legibly on CRFs supplied for each subject or directly inputted into an electronic system or any combination thereof.

11.3 Case Report Forms

The study CRF will be the primary data collection instrument for the study. All data requested on the CRF will be recorded. All missing data will be explained. Questions will have a response option for "Subject chose not to answer" or "Not applicable".

CRF List:

Sociodemographics
ACP Knowledge
ACP Engagement

Confidence in future care
Communication satisfaction
Decisional satisfaction
Decisional conflict

11.4 Study Records Retention

Study records, both paper and electronic versions, will be retained, per BMC policy, for at least seven years after completion of the study.

11.5 Data Management

Boston Medical Center will serve as the study data repository. A dedicated REDCap database housed at BMC will be used to manage randomization and survey data entry across all sites. Data will be regularly checked for errors and completeness.

Survey Data

Survey data from each of the clinical sites will be transmitted via secure, institutionally approved methods to Boston Medical Center. Identifying information in REDCap will be limited to only what is necessary for study procedures, and these will only be accessed to conduct study activities (contact information for study interviews). According to standard REDCap protocols, all access will be subject to monitoring and reporting. Assurance of confidentiality of information will be made to all subjects. Data will be handled with the same confidentiality accorded to patients' medical records.

Natural Language Processing (NLP) Data

The RA and site-PI at each of our two sites, where data is being collected, will extract data every two months from the EHR and surveys. Each site will maintain and adhere to the process and procedures for the protection of human subjects and protected health information (PHI) for their covered entities. All data collected by the RAs will be stored in password protected servers.

Participant identifiers will be kept in separate password protected files and a third linking file will be maintained. The linking file will also be password protected, access will be minimized, and a logging feature will be used to identify each user and instance of use. Only the minimum amount of PHI necessary will be collected from study participants. NLP data from each of the sites will be processed locally and then a HIPAA LDS of these data will be transferred via secure institutionally approved methods to Dana Farber Cancer Institute (DFCI) for data management and then to BMC to be merged with the rest of the study data repository. Data stored on the Dana Farber server will reside there only for the periods they are required to be there for study usage. Data will be securely removed from these servers on a per-item basis. Removed data will be securely transferred to BMC long-term servers for storage.

Specific procedures protecting subject confidentiality will be as follows:

1. Access to data files will be secured with a password-filing system (that logs entry) and is restricted to authorized staff only.
2. Necessary hard-copy records containing study data of any type will be kept in locked files.
3. Master lists linking subject information with ID number will be numbered consecutively and prepared before data collection (to ensure accurate accounting). These lists will be kept locked, in duplicate, with access only by the PIs and the other investigators at the site.
4. All project staff will sign an oath of confidentiality to ensure their understanding of the terms of confidentiality required. They will be trained in specific procedures to ensure confidentiality.
5. Sign-out procedures for all access to data files will be strictly enforced.
6. All reports and publications will preserve participants' anonymity.

12 Statistical Plan

12.1 Study Hypotheses

Aim 1: To test the effects of a PCE video intervention leveraging video decision aids on the quality of end-of-life care. We will conduct a SW-CRT to evaluate intervention effectiveness by comparing the following outcomes among 15,000 hospitalized patients: ACP documentation; preferences for resuscitation; palliative care consults; and, hospice use. **Hypotheses:** *A higher proportion of patients in the intervention phase (vs. control) will: (1) complete advance care plans (primary outcome), (2) have documented resuscitation preferences, (3) have palliative care consults, (4) enroll in hospice over the course of one year of follow-up, and (5) have documented health care proxies.*

Aim 2: To characterize caregiver-centered outcomes of patients with ADRD/Delirium, including: (1) knowledge, (2) confidence in future care, (3) communication satisfaction, (4) decisional satisfaction, and (5) decisional conflict in 600 caregivers of patients with ADRD/Delirium admitted to the hospital. **Hypothesis:** *Intervention phase caregivers of patients with ADRD/Delirium (vs. control) will have higher knowledge, confidence, communication satisfaction, decisional satisfaction, and lower decisional conflict.*

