Population:	
Aim 1: Patients ≥ 65 years admitted to one of the study inpatient units
 
Aim 2a: Any patient ≥ 18 years admitted to one of the study inpatient units with ADRD/delirium
 
Aim 2b: Adult Caregiver of any patient in aim 2a

Intervention:	Palliative Care Educator using video decision aid shown at time of admission to patients/caregivers in wards/units randomized to the intervention phase
Objectives:	The overall objective of the present proposal is to reduce the burden of COVID-19 and advanced illness and its consequences for an aging U.S. population.
Design/Methodology:	This project is a multi-center stepped wedge cluster randomized trial of an advance care planning (ACP) video intervention (vs. standard of care) using a Palliative Care Educator among patients ≥ 65 years OR any patient ≥ 18 years old with ADRD regardless of age admitted to one of the study inpatient units
Total Study Duration:	2 years
Subject Participation Duration:	EHR data collection during the 16 months of enrollment (2 months baseline plus 14 months intervention steps). EHR data abstracted for one year after the end of the 16 months of enrollment.

3 Background/Rationale & Purpose

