4.2.2 Secondary Outcome Measures

Secondary outcomes include:

- Code status preferences (Aim 1)
- Use of palliative care consult/services (Aim 1)
- Hospice use (Aim 1)
- Health Care Proxy (Aim 1)

Secondary outcomes related to Aim 2a (patients 18+ years admitted to one of the study inpatient units with ADRD/delirium) include:

- Documentation of ACP Preferences in Electronic Health Record

Secondary outcomes related to Aim 2b (caregivers of patients with ADRD/Delirium) include:

- ACP knowledge (Aim 2)
- Confidence in future care (Aim 2)
- Communication satisfaction (Aim 2)
- Decisional satisfaction (Aim 2)
- Decisional conflict (Aim 2)

5 Study Design

This is pragmatic SW-CRT of a PCE-led, video-assisted COVID-19 ACP intervention in inpatient-based units (3 medical-surgical wards, Medical ICU, Cardiac ICU, Neurology ICU, step-down unit) at two hospitals: BMC and North Shore University Hospital (Northwell Health). All inpatients ≥ 65 and all patients with ADRD/Delirium ≥ 18 who are hospitalized on a unit during the intervention phase will receive the intervention.

This 2-year study (2 month data collection and tool preparation, staff training and site standardization (we are already embedded in both health systems doing similar work; thus this

short timeframe is feasible); 16 months rolling recruitment and surveying; 2 months data cleaning and analysis, and 4 months manuscript preparation and dissemination of findings) will roll out the intervention to 14 randomized inpatient units at 2 sites. Every two months, an additional inpatient unit will be added to our intervention at each hospital, i.e., there will be seven waves or "steps"; for a total of 7 units at each hospital.

Consistent with a SW-CRT with two hospital units per step (cluster), prior to the collection of any data in the pre-intervention period, we will generate a set of uniform random numbers for each of the seven clusters to be assigned to a starting period for the study intervention. There will be eight study periods in total with a usual care period at the start of the study for all clusters. The first randomized intervention period will then begin in period two.

Cluster	Baseline	14 Months of Clustered Intervention Expansion							
	M0	M2	M4	M6	M8	M10	M12	M14	
1									
2									
3									
4									
5									
6									
7									

The data needed to assess the outcomes for all patients will be derived from each hospital's EHR (Aim 1).

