7.1 Subject Inclusion Criteria

Over the two years of the trial, we will examine data on approximately 15,000 patients ≥ 65 admitted to these 23* units for our primary and secondary outcomes (Aim 1). Given the pragmatic nature of this trial, our inclusion criteria are quite broad and consistent with the goal of pragmatic trials.

We will also survey caregivers of 600 patients with ADRD/Delirium to conduct a telephone administered survey for caregiver-centered outcomes (knowledge, confidence, communication satisfaction, decisional satisfaction, and decisional conflict) during the index hospitalization. Caregivers may or may not be designated as ADRD/Delirium legal surrogate decision maker for the patient (i.e., most patients with ADRD/Delirium do not have a legally designated representative.) Any adult identified in the EHR as the contact family member or friend will be eligible to partake in the caregiver survey. Half of surveys will be conducted during the control period; half during the intervention period. Caregivers will be either English- or Spanish-speaking adults, which are the languages in which our surveys are validated. For patients in the control group, surveys will be completed during the hospital stay or within 1 week of discharge. For patients in the intervention group, the survey will be completed AFTER the PCE intervention, and up to 1 week after discharge.

*14 units (7 per hospital) will be included in the stepped wedge trial, an additional 9 units (3 at BMC and 6 at NorthShore) will be used to recruit additional control participants only. These additional units were added due to low recruitment at the start of the study and the decreasing number of control units as the stepped wedge design progresses. The target enrollment of 600 caregivers is still accurate.

Adding delirium to the list of eligible diagnoses will also increase the potential number of eligible subjects. The surveys are applicable to the caregiver of any patient who is not capable of making their own health decisions; this includes patients who are experiencing any sort of memory or cognitive decline.

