Every 2 months (the size of each step; 1 baseline + 7 steps = 8 data transfers) the outcomes of interest using NLP will be transferred to our data collection site (DFCI). Data on the following outcomes will be collected until the end of the study period.

- ACP discussion (e.g., goals-of-care discussion, advance directive, MOLST/POLST, code status, etc.)
- Resuscitation preferences
- Palliative care consults
- Hospice Use
- Health care proxy discussion

As stated above, direct identifiers will be held at each respective site (BMC researchers can see BMC identifiers but not North Shore University Hospital's identifiers, and vice versa.) The risks will be minimal as the data will be stored and analyzed on a HIPAA secure cluster at each site. None of the data will be stored in paper form. The data and identifiers will be kept for seven years after the end of the study period on the HIPAA secure cluster computer at each site. After the seven years, all HIPAA identifiers and all linking codes will be permanently destroyed in accordance with regulation.

NLP Validation

Prior to the use of NLP for outcome assessment in this trial, we will entrain and validate the NLP process for each of our two study sites. Specifically, we will use historic note data from a sample of 20 patients from each site who meet enrollment criteria. We will then measure the validity of this process by comparing results from human assisted NLP to a human chart review. The goal of the keyword library validation process is to ensure that the keyword library and abstraction guidelines accurately represent the language used to communicate information associated study outcomes. The semi-automated note annotation process will be cross-validated across both sites. Clinical notes will be the substrate of this process and must be requested from each site's clinical data warehouse.

Each site will ensure that the appropriate IRB and Data Sharing protocols are in place before this activity begins.

Chart Review

EHR data will be extracted by manual chart review on all Aim 2a patients whose caregiver completes a survey (2b). This survey will be limited to the inpatient stay that generated the survey, and include the following elements for collection of secondary outcomes:

- DNR/DNI order
- MOLST/POLST filed
- Resuscitation/Intubation preferences
- Health Care Proxy specified
- Palliative Care Consult during hospitalization

- Discharge Disposition

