distributions of the uncertainty and knowledge scale scores, the outcomes of interest between intervention and usual care subjects, as well as the distributional characteristics of all other salient study variables. We will generate descriptive statistics (means, standard deviations, quantiles for continuous variables; counts and percentages for categorical variables) and schematic plots (box-and-whisker, quantile-quantile plots). Given the nature of the cluster randomization that we will employ, we will utilize statistical analytic methods that take the correlated nature of the data into account as well as the influence of time to account for secular trends. In this study, we will examine both the health system and hospital unit as clustering variables, with the hospital unit as the primary clustering variable. We will compare the intervention and usual care groups on salient variables in order to assess balance in the distributions of these variables. Variables found to differ between the study groups will be further evaluated to assess their confounding effects of intervention vs. usual care differences on outcomes in multivariable analyses for correlated (clustered) data.

Aim 1. To test the combined effects of a COVID-19 ACP Educator-led, video-assisted palliative care intervention on rates of: ACP documentation; Medical orders for resuscitation preferences in the EHR; Palliative Care Consults; and, Hospice use. ***Hypothesis: A higher proportion of patients in the intervention phase (vs. control) will: complete ACP documentation (primary trial outcome), have documented orders for resuscitation preferences, have palliative care consults, and enroll in hospice.***

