We will conduct analyses related to potential effect modification as a step in our model validation process and to identify relationships that can be examined more fully in future research. Should interactions not be found to be statistically significant, we will fit a main effects-only model and use it to formally evaluate confounding by applying a change-in-estimates approach, with a 10% change in estimates being an initial screening criterion. **Secondary outcomes:** Similar procedures will be undertaken to assess intervention effects for the other EHR derived outcomes (documented orders for resuscitation preferences, palliative care consults, hospice enrollment, and documented health care proxies).

For our primary analysis, we will consider our primary outcome (ACP documentation) and our secondary outcomes (resuscitation preferences, palliative care, hospice use, and health care proxies) only for the patient's index hospitalization. However, because we expect some patients to have multiple rehospitalizations during the same step and may also include intervention time (i.e., crossover design), we will perform secondary analyses on all of our primary and secondary outcomes for each patient reviewing all EHR records from the index hospitalization of the patient until their death (or through study period). We will also perform stratified sensitivity analyses of patients who contribute only to control period vs. patients who contribute only to intervention period vs. those that contribute to both control and intervention periods.

We will conduct the above analyses on all Aim 1 and Aim 2a patients for the study primary and secondary outcomes.

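### The hospice hypothesis covers one year of follow-up, but no planned analysis is set to one year, and the study calendar conflicts on whether that year exists

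*Combined protocol and SAP*

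**What the plan says.** **Hypothesis.** Sections 4.1 and 12.1 both predict that a higher proportion of intervention-phase patients will "enroll in hospice over the course of one year of follow-up". This is the only Aim 1 hypothesis with a time horizon. Section 12.3 restates the Aim 1 hypothesis as patients who will "have documented orders for resuscitation preferences, have palliative care consults, and enroll in hospice", with no horizon.

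**Analysis.** Section 12.3 says the primary analysis will consider "our secondary outcomes (resuscitation preferences, palliative care, hospice use, and health care proxies) only for the patient's index hospitalization". The opening of Section 12.3 agrees: each subject contributes once, from the index stay. The one longer analysis is labelled secondary, covers all primary and secondary outcomes, and works by "reviewing all EHR records from the index hospitalization of the patient until their death (or through study period").

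**Calendar.** The synopsis gives a total duration of 2 years and also has "EHR data abstracted for one year after the end of the 16 months of enrollment". Section 5 describes a 2-year study with 2 months of preparation, 16 months of recruitment, then "2 months data cleaning and analysis, and 4 months manuscript preparation and dissemination of findings". Section 9 (NLP data collection) plans transfers "Every 2 months (the size of each step; 1 baseline + 7 steps = 8 data transfers") and collects outcomes until an undated end of the study period.

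**The concern.** A hypothesis, its outcome window and its analysis should describe the same quantity. Here the hypothesis is a one-year risk, the main analysis measures an in-hospital event, and the longer analysis measures an event over whatever time each patient happens to have. Two hospice results will exist, neither over one year, and nothing says which one tests hypothesis (4). That choice could then be made after the data are seen.

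The open-ended window has a further consequence in a stepped wedge. Control patients enrol earlier on average, so a common data cut gives them longer to reach hospice. Whether most intervention patients could have a one-year outcome at all depends on which section's calendar governs.

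**Working it through.** **Step 1. The plan's own calendar.** Section 5: 2 + 16 + 2 + 4 = 24 months, which reproduces the stated 2 years. Section 9: 8 transfers × 2 months = 16 months, the length of enrolment. Neither contains a follow-up year.

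**Step 2. The synopsis calendar.** Enrolment plus the follow-up year: 16 + 12 = 28 months. With Section 5's preparation phase first: 2 + 16 + 12 = 30 months. If Section 5's cleaning and dissemination phases both wait for it: 30 + 2 + 4 = 36 months. All exceed 24.

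**Step 3. Potential follow-up by phase.** Inputs are the Section 5 layout: 7 clusters and 8 two-month periods, with cluster k in control for periods 1 to k. Assumptions: equal, uniform enrolment per cluster-period, deaths ignored, 14 stepped-wedge units only.

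- Period j has 8 − j control clusters and j − 1 intervention clusters, so there are 28 control and 28 intervention cluster-periods.
- Mean control period: Σ j(8 − j)/28 = 84/28 = 3.0.
- Mean intervention period: Σ j(j − 1)/28 = 168/28 = 6.0.
- Gap in potential follow-up: 2 × (6.0 − 3.0) = 6.0 months, whatever the common cut.

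The midpoint of period j is enrolment month 2j − 1, so mean follow-up to a cut at enrolment month C is C − 5 for control and C − 11 for intervention. A cluster-period counts as having a full year when its last entrant does, that is, when 2j + 12 ≤ C. Study month is enrolment month plus 2, taking preparation as preceding enrolment.

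| Data cut | C | Mean follow-up, control vs intervention (months) | Full year available, control vs intervention |
|---|---|---|---|
| Study month 18 (enrolment ends) | 16 | 11 vs 5 | 13/28 = 46% vs 1/28 = 4% |
| Study month 24 (stated study end) | 22 | 17 vs 11 | 25/28 = 89% vs 10/28 = 36% |
| Study month 30 (synopsis year completed) | 28 | 23 vs 17 | 100% vs 100% |

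The cuts are assumptions, because the documents do not date the end of the study period.

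**Step 4. What a fixed window costs.** Cluster k switches at enrolment month 2k. A control patient enrolled in period j ≤ k is therefore at most 2(k − j + 1) months from the switch. This is 12 months or less whenever k − j ≤ 5, which is every control cluster-period except k = 7, j = 1: 27 of 28. A 12-month window thus carries nearly all control patients past their unit's switch, and a readmitted one may be exposed.

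**The case against.** The strongest reply is that the data plan already exists. If the synopsis year is carried out, every patient's first 12 months fall inside the all-records analysis; only a cap and a sentence tying the hypothesis to that analysis are missing. This stands. A reader might infer that a one-year hospice outcome is unobtainable, and the documents do not support that. Section 9's undated end of collection does not contradict the synopsis year either; the conflict lies in the synopsis's own 2-year total, Section 5's calendar and the count of eight transfers.

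A reader might also infer that the hospice comparison is biased by 6 months of unequal observation. That goes too far. The 6.0 months is unadjusted potential follow-up, not a bias in the planned estimate. With a common data cut, available follow-up is set by enrolment time, and Section 12.3 plans to account for time. Categorical period effects compare patients enrolled in the same two months and so can absorb most of the imbalance. What remains unadjusted would favour control, against the hypothesis.

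Two things survive the reply. Section 12.3 does not say how time will be modelled. And adjustment balances follow-up without turning a mixture of lengths into a one-year effect.

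**Conclusion.** The mismatch is real. Followed as written, the plan would answer a one-year hypothesis with either an index-stay result or a mixed-length one, on a calendar that disagrees with itself by at least 4 months (28 against 24). It should be corrected, but its reach is limited to one secondary outcome's hypothesis and to the all-records analysis. The primary outcome and the index-stay hospice analysis are not touched by unequal follow-up.

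The follow-up figures rest on equal enrolment per cluster-period, no deaths and the 14 randomized units. Section 7.1 says that "an additional 9 units (3 at BMC and 6 at NorthShore) will be used to recruit additional control participants only". A reader might infer that these units change the gap, but their place in Aim 1 is unclear: the section counts 23 units for Aim 1, while its footnote speaks of recruitment and the caregiver target. No start date is given. They are left out here and do not alter the conclusion.

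**What to change.** State one hospice window and use it in Sections 4.1 and 12.1 and in both places in Section 12.3. There are two ways to do this.

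- **(a) Index stay.** Reword hypothesis (4) to hospice use during the index hospitalization. This is a wording change and fits the current 24 months. The cost is fewer hospice events.
- **(b) One year.** If the synopsis follow-up year is kept, name a hospice analysis capped at 12 months from index admission. The cap is identical in both phases, patients are analysed by the phase of their index stay, and period is fitted as a categorical effect. This needs a data cut at about study month 30. It also dilutes the contrast, because the unit switches within 12 months for 27 of 28 control cluster-periods. Section 12.3's stratified sensitivity analyses (control only, intervention only, both) should be reported alongside. The index-stay primary analysis need not wait for this cut.

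Use the same capped window for the other outcomes in the all-records analysis, since they share the open-ended follow-up. Under either option, reconcile study duration, follow-up and data-cut date across the synopsis, Section 5 and Section 9, leaving time for analysis after the cut.
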